| Congenital visual acuity reduced | Iris transillumination defect | Retinal vasculitis |
| Congenital vitreous anomaly | Iris vascular disorder | Retinal vein occlusion |
| Conjunctival abrasion | Iritis | Retinal vein thrombosis |
| Conjunctival adhesion | Irlen syndrome | Retinal vessel avulsion |
| Conjunctival bleb | IRVAN syndrome | Retinal white without pressure |
| Conjunctival cyst | IVth nerve disorder | Retinitis |
| Conjunctival degeneration | IVth nerve injury | Retinitis histoplasma |
| Conjunctival deposit | IVth nerve paralysis | Retinitis pigmentosa |
| Conjunctival discolouration | Kayser-Fleischer ring | Retinitis viral |
| Conjunctival disorder | Kearns-Sayre syndrome | Retinoblastoma |
| Conjunctival erosion | Keratic precipitates | Retinopathy congenital |
| Conjunctival filtering bleb leak | Keratitis | Retinopathy haemorrhagic |
| Conjunctival follicles | Keratitis bacterial | Retinopathy hypertensive |
| Conjunctival granuloma | Keratitis fungal | Retinopathy hyperviscosity |
| Conjunctival haemorrhage | Keratitis interstitial | Retinopathy of prematurity |
| Conjunctival hyperaemia | Keratitis sclerosing | Retinopathy proliferative |
| Conjunctival irritation | Keratitis viral | Retinopathy sickle cell |
| Conjunctival laceration | Keratitis-ichthyosis-deafness syndrome | Retinopathy solar |
| Conjunctival lymphangiectasia | Keratoconjunctivitis measles | Retinoschisis |
| Conjunctival melanoma | Keratoconus | Retinoschisis congenital |
| Conjunctival neoplasm | Keratomalacia | Retro-orbital neoplasm |
| Conjunctival oedema | Keratopathy | Rhegmatogenous retinal detachment |
| Conjunctival opacity | Keratorhexis | Rheumatoid scleritis |
| Conjunctival pallor | Keratosis gonococcal | Romana's sign |
| Conjunctival pigmentation | Keratouveitis | Ross syndrome |
| Conjunctival primary acquired melanosis | Koeppe nodules | Saccadic eye movement |
| Conjunctival retraction | Lacrimal atrophy | Schlemm's canal obstruction |
| Conjunctival scar | Lacrimal cyst | Scintillating scotoma |

| SOC Eye Disorders | SOC Eye Disorders | SOC Eye Disorders |
|------------------------------------|---|--|
| Conjunctival telangiectasia | Lacrimal disorder | Scleral cyst |
| Conjunctival ulcer | Lacrimal duct neoplasm | Scleral degeneration |
| Conjunctival vascular disorder | Lacrimal duct pigmentation | Scleral deposits |
| Conjunctivalisation | Lacrimal fistula | Scleral discolouration |
| Conjunctivitis | Lacrimal gland abscess | Scleral disorder |
| Conjunctivitis allergic | Lacrimal gland enlargement | Scleral haemorrhage |
| Conjunctivitis bacterial | Lacrimal haemorrhage | Scleral hyperaemia |
| Conjunctivitis chlamydial | Lacrimal mucocoele | Scleral oedema |
| Conjunctivitis fungal | Lacrimal passage granuloma | Scleral pigmentation |
| Conjunctivitis gonococcal neonatal | Lacrimal punctum agenesis | Scleral thinning |
| Conjunctivitis tuberculous | Lacrimal punctum enlarged | Scleritis |
| Conjunctivitis viral | Lacrimal sac cellulitis | Scleritis allergic |
| Conjunctivochalasis | Lacrimal structural disorder | Scleromalacia |
| Contact lens acute red eye | Lacrimal structure injury | Seasonal allergy |
| Contact lens intolerance | Lacrimation decreased | Septo-optic dysplasia |
| Corectopia | Lacrimation disorder | Silent sinus syndrome |
| Cornea verticillata | Lacrimation increased | Sjogren's syndrome |
| Corneal abrasion | Lagophthalmos | Slipped extraocular muscle |
| Corneal abscess | Laurence-Moon-Bardet-Biedl syndrome | Spherophakia |
| Corneal bleeding | Leber's congenital amaurosis | Spontaneous hyphaema |
| Corneal cyst | Lecithin-cholesterol acyltransferase deficiency | Staphylococcal blepharitis |
| Corneal decompensation | Lens abnormality, congenital | Staphyloma |
| Corneal defect | Lens discolouration | Stargardt's disease |
| Corneal degeneration | Lens dislocation | Stickler's syndrome |
| Corneal deposits | Lens disorder | Strabismus |
| Corneal disorder | Lenticular injury | Strabismus congenital |
| Corneal dystrophy | Lenticular opacities | Sturge-Weber syndrome |
| Corneal endothelial cell loss | Lenticular pigmentation | Subacute myelo-optic neuropathy |
| Corneal endotheliitis | Leukaemic retinopathy | Subconjunctival cyst |
| Corneal epithelial microcysts | Leukocoria | Subretinal fibrosis |
| Corneal epithelial wrinkling | Lid lag | Subretinal haematoma |
| Corneal epithelium defect | Lid margin discharge | Sudden visual loss |
| Corneal erosion | Lid sulcus deepened | Superficial injury of eye |
| Corneal exfoliation | Ligneous conjunctivitis | Superior corneal epithelial arcuate lesion |
| Corneal flap complication | Limbal stem cell deficiency | Superior limbic keratoconjunctivitis |
| Corneal graft rejection | Limbal swelling | Susac's syndrome |

| SOC Eye Disorders | SOC Eye Disorders | SOC Eye Disorders |
|--|--------------------------------------|---|
| Corneal hypertrophy | Lipaemia retinalis | Swollen tear duct |
| Corneal infection | Lipodermoid tumour | Symblepharon |
| Corneal infiltrates | Loss of visual contrast sensitivity | Sympathetic ophthalmia |
| Corneal irritation | Macrocornea | Tear discolouration |
| Corneal lesion | Macular cyst | Temporal arteritis |
| Corneal leukoma | Macular degeneration | Tenon's cyst |
| Corneal neovascularisation | Macular dystrophy congenital | Terrien's marginal degeneration |
| Corneal oedema | Macular fibrosis | Thermal burns of eye |
| Corneal opacity | Macular hole | Thyrotoxic crisis |
| Corneal opacity congenital | Macular ischaemia | Tilted disc syndrome |
| Corneal perforation | Macular oedema | Tolosa-Hunt syndrome |
| Corneal pigmentation | Macular opacity | Toxic anterior segment syndrome |
| Corneal scar | Macular pigmentation | Toxic cataract |
| Corneal staphyloma | Macular pseudohole | Toxic optic neuropathy |
| Corneal striae | Macular rupture | Toxocariasis |
| Corneal thickening | Macular scar | Trachoma |
| Corneal thinning | Macular vasospasm | Tractional retinal detachment |
| Corneal touch | Maculopathy | Traumatic iritis |
| Corneal warpage | Madarosis | Trichiasis |
| Corneoconjunctival intraepithelial neoplasia | MAGIC syndrome | Trichomegaly |
| Cortical visual impairment | Malignant exophthalmos | Triple A syndrome |
| Cri du Chat syndrome | Malignant glaucoma | Trisomy 13 |
| Crocodile tears syndrome | Malignant melanoma of eyelid | Trisomy 22 |
| Cryptophthalmos | Malignant neoplasm of choroid | Tuberculosis of eye |
| Cutaneous horn of eyelid | Malignant neoplasm of conjunctiva | Tubulointerstitial nephritis and uveitis syndrome |
| Cyanopsia | Malignant neoplasm of cornea | Tunnel vision |
| Cyclitic membrane | Malignant neoplasm of eye | Uhthoff's phenomenon |
| Cyclitis | Malignant neoplasm of eyelid | Ulcerative keratitis |
| Cyclopia | Malignant neoplasm of lacrimal duct | Usher's syndrome |
| Cycloplegia | Malignant neoplasm of lacrimal gland | Uveal prolapse |
| Cystic eyeball, congenital | Malignant neoplasm of orbit | Uveitic glaucoma |
| Cystoid macular oedema | Malignant neoplasm of retina | Uveitis |
| Cytomegalovirus chorioretinitis | Marcus Gunn syndrome | Uveitis-glaucoma-hyphaema syndrome |
| Dacryoadenitis acquired | Marfan's syndrome | Varicella keratitis |
| Dacryocanaliculitis | Meibomian gland discharge | Venous stasis retinopathy |

| SOC Eye Disorders | SOC Eye Disorders | SOC Eye Disorders |
|---|--|--|
| Dacryocystitis | Meibomian gland dysfunction | Vernal keratoconjunctivitis |
| Dacryolith | Meibomianitis | Vestibular nystagmus |
| Dacryostenosis acquired | Metallosis of globe | Viral corneal ulcer |
| Dacryostenosis congenital | Metamorphopsia | Viral keratouveitis |
| Dark circles under eyes | Metastases to eye | Viral uveitis |
| Deep anterior chamber of the eye | Metastatic ocular melanoma | Vision abnormal neonatal |
| Deformity of orbit | Microcornea | Vision blurred |
| Delayed dark adaptation | Microphtalmos | Visual acuity reduced |
| Delayed light adaptation | Microvascular cranial nerve palsy | Visual acuity reduced transiently |
| Delayed visual maturation | Mikulicz's disease | Visual brightness |
| Dellen | Mikulicz's syndrome | Visual cortex atrophy |
| Deposit eye | Millard-Gubler syndrome | Visual field defect |
| Detached Descemet's membrane | Miller Fisher syndrome | Visual impairment |
| Developmental glaucoma | Miosis | Visual pathway disorder |
| Diabetic blindness | Mittendorf dot | Visual perseveration |
| Diabetic eye disease | Morning glory syndrome | Visual snow syndrome |
| Diabetic glaucoma | Mycotic corneal ulcer | Vitamin A deficiency eye disorder |
| Diabetic keratopathy | Mycotic endophthalmitis | Vitamin A deficiency related conjunctival disorder |
| Diabetic ophthalmoplegia | Mydriasis | Vitamin A deficiency related corneal disorder |
| Diabetic retinal oedema | MYH9-related disease | VIth nerve disorder |
| Diabetic retinopathy | Myopia | VIth nerve injury |
| Diabetic uveitis | Myopic chorioretinal degeneration | VIth nerve paralysis |
| Diffuse lamellar keratitis | Myopic disc | VIth nerve paresis |
| Diffuse uveal melanocytic proliferation | Narrow anterior chamber angle | Vitreal cells |
| Diplopia | Necrotising herpetic retinopathy | Vitreomacular interface abnormal |
| Disorder of globe | Necrotising retinitis | Vitreous abscess |
| Disorder of orbit | Necrotising scleritis | Vitreous adhesions |
| Distichiasis | Neoplasm of cornea unspecified malignancy | Vitreous cyst |
| Dry age-related macular degeneration | Neoplasm of orbit | Vitreous degeneration |
| Dry eye | Neovascular age-related macular degeneration | Vitreous detachment |
| Duane's syndrome | Neurologic neglect syndrome | Vitreous disorder |
| Dyschromatopsia | Neurological eyelid disorder | Vitreous fibrin |
| Dysmetropsia | Neuromyelitis optica pseudo relapse | Vitreous floaters |
| Eales' disease | Neuromyelitis optica spectrum disorder | Vitreous haematoma |

| SOC Eye Disorders | SOC Eye Disorders | SOC Eye Disorders |
|------------------------------|---|---|
| Eccentric fixation | Neuropathy, ataxia, retinitis pigmentosa syndrome | Vitreous haemorrhage |
| Ectropion | Neurotrophic keratopathy | Vitreous haze |
| Ectropion uveae | Nictitating spasm | Vitreous injury |
| Eczema eyelids | Night blindness | Vitreous loss |
| Emanuel syndrome | Non-infectious endophthalmitis | Vitreous opacities |
| Endocrine ophthalmopathy | Noninfective chorioretinitis | Vitreous prolapse |
| Endophthalmitis | Noninfective conjunctivitis | Vitritis |
| Enophthalmos | Noninfective retinitis | Vogt-Koyanagi-Harada syndrome |
| Enophthalmos traumatic | Normal tension glaucoma | Waardenburg syndrome |
| Entropion | Norrie's disease | Wagner's disease |
| Entropion congenital | Nystagmus | Weill-Marchesani syndrome |
| Episcleral hyperaemia | Ocular albinism | Wildervanck syndrome |
| Episcleritis | Ocular cancer metastatic | Winchester syndrome |
| Erythema of eyelid | Ocular discomfort | Wolfram syndrome |
| Erythropsia | Ocular dysmetria | Wyburn Mason's syndrome |
| Eversion of lacrimal punctum | Ocular fistula | Xanthopsia |
| Excessive eye blinking | Ocular haemangiopericytoma | Xerophthalmia |
| Excessive ocular convergence | Ocular hyperaemia | Zika virus associated ocular birth defect |
| Exfoliation glaucoma | Ocular hypertension | Ocular icterus |

5.9 Minimum Critical Toxicities

Minimum Critical Toxicity search strategies are per SMQs and utilize MedDRA 21.0. As SMQs are standardized lists of PTs per MedDRA version, the individual SMQ PTs are not enumerated further within this document. The search strategies described below will be used to identify cases for analysis purposes and are not intended to be used to calculate frequencies of adverse drug reactions.

Table 11: Table of Minimal Critical Toxicities and SMQ Search Strategies

| Minimal Critical Toxicity | Search Strategy |
|---------------------------|--|
| Hepatotoxicity | 
Biliary system related investigations, signs, and symptoms SMQ [narrow, broad]Cholestasis and jaundice of hepatic origin SMQ [narrow, broad]Hepatic failure, fibrosis and cirrhosis and other liver damage-related conditions SMQ [narrow, broad]Hepatitis, non-infectious SMQ [narrow, broad]Liver related investigations, signs and symptoms SMQ [narrow, broad] |
| Cardiac Toxicity | 
Torsade de Pointes / QT prolongation SMQ [narrow, broad] |
| Nephrotoxicity | 
Acute renal failure SMQ [narrow, broad] |
| Haematologic Toxicities | 
Haematopoietic cytopenias affecting more than one type of blood cell SMQ [narrow, broad]Haematopoietic erythropenia SMQ [narrow, broad]Haematopoietic leukopenia SMQ [narrow, broad]Haematopoietic thrombocytopenia SMQ [narrow, broad] |

5.10 CYP3A4 Inhibitors and Inducers

The list of CYP3A4 inducers and inhibitors are retrieved from the Drug Bank ([Wishart 2017](#)). Terms are coded based on WHODrug Enhanced + Herbals (HD/DDE) Mar2018 B3 global.

The coded concomitant medications which contained below preferred terms will be marked according to type (inhibitor/inducer) and category (moderate/strong) with the exception that medication administered through topical, optic or aural routes will not be considered as inducers or inhibitors.

| Type | Category | Preferred Name/Generic Name | Type | Category | Preferred Term |
|-----------|----------|-----------------------------|---------|----------|----------------|
| Inhibitor | Moderate | AMIODARONE | Inducer | Moderate | AVASIMIBE |
| Inhibitor | Moderate | AMPRENAVIR | Inducer | Moderate | BEXAROTENE |
| Inhibitor | Moderate | ANASTROZOLE | Inducer | Moderate | BOSENTAN |
| Inhibitor | Moderate | APREPITANT | Inducer | Moderate | DABRAFENIB |
| Inhibitor | Moderate | BARNIDIPINE | Inducer | Moderate | EFAVIRENZ |
| Inhibitor | Moderate | BENIDIPINE | Inducer | Moderate | ETRAVIRINE |
| Inhibitor | Moderate | CLOBAZAM | Inducer | Moderate | MIFEPRISTONE |
| Inhibitor | Moderate | CLOZAPINE | Inducer | Moderate | MODAFINIL |
| Inhibitor | Moderate | CRIZOTINIB | Inducer | Moderate | NAFCILLIN |
| Inhibitor | Moderate | DANAZOL | Inducer | Strong | APALUTAMIDE |
| Inhibitor | Moderate | DESVENLAFAZINE | Inducer | Strong | CARBAMAZEPINE |
| Inhibitor | Moderate | DILTIAZEM | Inducer | Strong | DEXAMETHASONE |
| Inhibitor | Moderate | DIMETHYL SULFOXIDE | Inducer | Strong | ENZALUTAMIDE |
| Inhibitor | Moderate | DRONEDARONE | Inducer | Strong | FOSPHENYTOIN |
| Inhibitor | Moderate | ERYTHROMYCIN | Inducer | Strong | LUMACRAFTOR |

| Type | Category | Preferred Name/Generic Name | Type | Category | Preferred Term |
|-----------|----------|-----------------------------|---------|----------|----------------------|
| Inhibitor | Moderate | FLUCONAZOLE | Inducer | Strong | MIDOSTAURIN |
| Inhibitor | Moderate | FLUVOXAMINE | Inducer | Strong | MITOTANE |
| Inhibitor | Moderate | FOSAMPRENAVIR | Inducer | Strong | NEVIRAPINE |
| Inhibitor | Moderate | FOSNETUPITANT | Inducer | Strong | OXCARBAZEPINE |
| Inhibitor | Moderate | FUSIDIC ACID | Inducer | Strong | PENTOBARBITAL |
| Inhibitor | Moderate | HALOPERIDOL | Inducer | Strong | PHENOBARBITAL |
| Inhibitor | Moderate | IMATINIB | Inducer | Strong | PHENYTOIN |
| Inhibitor | Moderate | INDALPINE | Inducer | Strong | PRIMIDONE |
| Inhibitor | Moderate | ISAVUCONAZOLE | Inducer | Strong | RIFAMPICIN |
| Inhibitor | Moderate | ISAVUCONAZONIUM | Inducer | Strong | RIFAMYCIN |
| Inhibitor | Moderate | ISONIAZID | Inducer | Strong | RIFAXIMIN |
| Inhibitor | Moderate | ISRADIPINE | Inducer | Strong | RIMEXOLONE |
| Inhibitor | Moderate | LINAGLIPTIN | Inducer | Strong | HYPERICUM PERFORATUM |
| Inhibitor | Moderate | LOVASTATIN | Inducer | Strong | GLUCOCORTICOIDS |
| Inhibitor | Moderate | LULICONAZOLE | | | |
| Inhibitor | Moderate | MICONAZOLE | | | |
| Inhibitor | Moderate | MIFEPRISTONE | | | |
| Inhibitor | Moderate | MILNACIPRAN | | | |
| Inhibitor | Moderate | NETUPITANT | | | |
| Inhibitor | Moderate | NICARDIPINE | | | |
| Inhibitor | Moderate | NILVADIPINE | | | |
| Inhibitor | Moderate | PAROXETINE | | | |
| Inhibitor | Moderate | PRIMAQUINE | | | |
| Inhibitor | Moderate | RISPERIDONE | | | |
| Inhibitor | Moderate | SERTRALINE | | | |
| Inhibitor | Moderate | SIMEPREVIR | | | |
| Inhibitor | Moderate | TIOCONAZOLE | | | |
| Inhibitor | Moderate | VENETOCLAX | | | |
| Inhibitor | Moderate | VENLAFAXINE | | | |
| Inhibitor | Moderate | VERAPAMIL | | | |
| Inhibitor | Moderate | ZIMELDINE | | | |
| Inhibitor | Moderate | ZIPRASIDONE | | | |
| Inhibitor | Strong | ATAZANAVIR | | | |
| Inhibitor | Strong | BOCEPREVIR | | | |
| Inhibitor | Strong | CLARITHROMYCIN | | | |
| Inhibitor | Strong | CLOTRIMAZOLE | | | |
| Inhibitor | Strong | COBICISTAT | | | |
| Inhibitor | Strong | CONIVAPTAN | | | |

| Type | Category | Preferred Name/Generic Name | Type | Category | Preferred Term |
|-----------|----------|-----------------------------|------|----------|----------------|
| Inhibitor | Strong | CURCUMIN | | | |
| Inhibitor | Strong | DANOPREVIR | | | |
| Inhibitor | Strong | DARUNAVIR | | | |
| Inhibitor | Strong | DELAVIRDINE | | | |
| Inhibitor | Strong | DILTIAZEM | | | |
| Inhibitor | Strong | ECONAZOLE | | | |
| Inhibitor | Strong | EFAVIRENZ | | | |
| Inhibitor | Strong | ELVITEGRAVIR | | | |
| Inhibitor | Strong | ERGOTAMINE | | | |
| Inhibitor | Strong | IDEALISISB | | | |
| Inhibitor | Strong | INDINAVIR | | | |
| Inhibitor | Strong | ITRACONAZOLE | | | |
| Inhibitor | Strong | KETOCONAZOLE | | | |
| Inhibitor | Strong | LOPERAMIDE | | | |
| Inhibitor | Strong | LOPINAVIR | | | |
| Inhibitor | Strong | MIBEFRADIL | | | |
| Inhibitor | Strong | MIDOSTAURIN | | | |
| Inhibitor | Strong | NALOXONE | | | |
| Inhibitor | Strong | NEFAZODONE | | | |
| Inhibitor | Strong | NELFINAVIR | | | |
| Inhibitor | Strong | NILOTINIB | | | |
| Inhibitor | Strong | POSACONAZOLE | | | |
| Inhibitor | Strong | RIBOCICLIB | | | |
| Inhibitor | Strong | RITONAVIR | | | |
| Inhibitor | Strong | SAQUINAVIR | | | |
| Inhibitor | Strong | STIRIPENTOL | | | |
| Inhibitor | Strong | TELAPREVIR | | | |
| Inhibitor | Strong | TELITHROMYCIN | | | |
| Inhibitor | Strong | TERFENADINE | | | |
| Inhibitor | Strong | TIPRANAVIR | | | |
| Inhibitor | Strong | TROLEANDOMYCIN | | | |
| Inhibitor | Strong | VORICONAZOLE | | | |

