# Management of Alopecia, Palmar-Plantar Erythrodysesthesia, Paronychia, and Stomatitis

Recommendations for management (not required per protocol) of alopecia, palmarplantar erythrodysesthesia syndrome, paronychia (adapted from Segaert 2005), and stomatitis (adapted from Rugo 2017) are provided in Table 6. These are guidelines only and institutional guidelines should be followed where applicable.

Table 6: Recommended Management of Alopecia, Palmar-Plantar Erythrodysesthesia Syndrome, Paronychia, and Stomatitis

Alopecia	
Grade 1	Continue study drug
	• Minoxidil 5% (OTC) solution or foam once daily to scalp
Grade 2	Continue study drug
	Minoxidil 5% (OTC) solution or foam twice daily to scalp
	Fluocinonide 0.05% solution daily to scalp
	antar erythrodysesthesia syndrome
Grade 0/1	Continue study drug
	Urea 20% or ammonium lactate 12% lotions BID to hands and feet
Grade 2	Continue study drug
	• Urea 20% or ammonium lactate 12% BID to hands and feet
	Fluocinonide 0.05% cream BID to hands and feet
Grade 3	Hold study drug until resolved to Grade ≤1
	• Urea 20% or ammonium lactate 12% BID to hands and feet
	• Fluocinonide 0.05% cream BID to hands and feet
Paronychi	
Grade 1	Continue study drug
	Clindamycin 1% solution around and under nails TID
	Soak for 15 minutes daily in white vinegar in tap water (1:1)
Grade 2	Continue study drug
	Obtain bacterial cultures to confirm sensitivity to antimicrobial
	Cefadroxil 500 mg BID or TMP/SMX DS BID for 14 days
	Soak for 15 minutes daily in white vinegar in tap water (1:1)
	Dermatology consultation
Grade 3	Hold study drug until resolved to Grade ≤1
	Obtain bacterial cultures to confirm sensitivity to antimicrobial
	Cefadroxil 500 mg BID or TMP/SMX DS BID for 14 days
G:	Dermatology consultation
Stomatitis	T
Grade 1	Continue study drug
G 1 A	Dexamethasone elixir 0.5 mg/mL swish and spit 1 teaspoon (5mL) TID.
Grade 2	Continue study drug
G 1 2	Dexamethasone elixir 0.5 mg/mL swish and spit 1 teaspoon (5mL) TID
Grade 3	Hold study drug until resolved to Grade ≤1
	Dexamethasone elixir 0.5 mg/mL swish and spit 1 teaspoon (5 mL) TID.
	Clotrimazole 10 mg lozenges QD

BID=2 times daily; OTC=over-the-counter; QD=once daily; TID=3 times daily; TMP/SMX DS=sulfamethoxazole and trimethoprim

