## 14 APPENDICES

# 14.1 Appendix 1: List of concomitant medications

In general, the use of any concomitant medication deemed necessary for the care of the patient is permitted in this study, except as specifically prohibited below. Combination administration of study drugs could result in drug-drug interactions (DDI) that could potentially lead to reduced activity or enhanced toxicity of the concomitant medication and/or BGJ398.

Confidential

The following lists in Table 15 are based on the Indiana University School of Medicine's "Clinically Relevant" Table (Flockhart TableTM; Flockhart 2007) and supplemented with the FDA Draft guidance and the online database Drugbank.ca. Note: this may not be an exhaustive list of medications, investigator should use this list as a guide.

Table 15: Drugs to be used with caution while on study

Category	Drug Names	
CYP3A substrates with narrow therapeutic index	alfentanil, cyclosporine, diergotamine, dihydroergotamine, ergotamine, fentanyl, sirolimus, tacrolimus, terfenadine, warfarin sodium or any other coumadin-derivative anticoagulants, direct thrombin inhibitors (eg, argatroban), and Factor Xa inhibitors (eg, rivaroxaban)	
Moderate inhibitors of CYP3A4	amprenavir, aprepitant, atazanavir, cannabinoids, casopitant, cimetidine, ciprofloxacin, darunavir, diltiazem, fosamprenavir, imatinib, metronidazole, Schisandra sphenanthera, sertraline, suboxone, tofisopam, verapamil, zafirlukast	
Moderate inducers of CYP3A4	bosentan, cotrimoxazole, efavirenz, etravirine, ethosuximide, genistein, metyrapone, mexiletine, modafinil, nafcillin, talviraline, tipranavir	
Medications which alter the pH of the GI tract a,b	antacids, H 2 antagonists (eg, ranitidine), proton-pump inhibitors (eg, omeprazole)	
Medications that have possible risk of TdP/QT prolongation		
Medications that have conditional risk of TdP/QT prolongation	amitriptyline, amisulpride, ciprofloxacin, clomipramine, desipramine, diphenhydramine, doxepin, fluoxetine, galantamine, imipramine, nortriptyline, paroxetine, protriptyline, sertraline, solifenacin, trazodone, trimethoprimsulfa, trimipramine	

Category	Drug Names

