# 14.2 Appendix 2: List of prohibited medications

Table 16: List of prohibited medications and substances while on study

Category	Drug name
Strong inhibitors of CYP3A4	clarithromycin, conivaptan, fluconazole, fluvoxamine, indinavir, itraconazole, ketoconazole, lopinavir, mibefradil, miconazole, nefazodone, nelfinavir, norfloxacin, posaconazole, ritonavir, saquinavir, telithromycin, voriconazole
	grapefruit, grapefruit juice, grapefruit hybrids, pomegranates, star fruits, pomelos, Seville oranges or products containing juice of these fruits
Strong inducers of CYP3A4	avasimibe, carbamazepine, nevirapine, phenobarbital, phenytoin, pioglitazone, primidone, rifabutin, rifampin, St. John's wort, troglitazone
Medications which increase serum phosphorus and/or calcium	calcium, parathyroid hormone, phosphate, vitamin D (including multivitamins containing vitamin D)

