The summaries of the efficacy variables may be repeated for the following subgroups:

- Lines of prior therapy (<=1 vs >1)
- Gender (male vs female)
- Age >=65 vs <65
- Region (North America vs Western Europe vs Asia)

Summaries for TEAEs will be repeated for the following subgroups:

- Gender (male vs female)
- Age group (>=65 vs <65)
- Region group (North America vs Western Europe vs Asia)
- BMI (<18.5 vs. >=18.5)
- Subjects who received strong CYP3A4 inhibitors vs moderate CYP3A4 inhibitors vs none (Section 5.10)

- Subjects who received strong CYP3A4 inducers vs moderate CYP3A4 inducers vs none (Section 5.10)

The list of strong CYP3A4 inhibitors and inducers is documented in Section 5.10.

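### SAP 5.10 gives no flag to 18 of the 59 drugs the protocol names as CYP3A4 inhibitors or inducers, so a patient whose only such drug is unlisted is tabulated as 'none' in the TEAE subgroups

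*SAP*

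**What the plan says.** **Protocol.** Appendix 1 (Table 15) lists moderate CYP3A4 inhibitors and inducers to be used with caution. Its inducer row reads "bosentan, cotrimoxazole, efavirenz, etravirine, ethosuximide, genistein, metyrapone, mexiletine, modafinil, nafcillin, talviraline, tipranavir", and its inhibitor row includes "cimetidine, ciprofloxacin, darunavir, diltiazem, fosamprenavir, imatinib, metronidazole". Appendix 2 (Table 16) lists strong inhibitors and inducers as prohibited; its inducer row includes "phenytoin, pioglitazone, primidone, rifabutin, rifampin". Table 6, the recommended management of skin and mucosal toxicity, gives this for Grade 2 and Grade 3 paronychia: "Cefadroxil 500 mg BID or TMP/SMX DS BID for 14 days".

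**SAP.** Section 2.2.8 says that efficacy subgroups may be repeated but that TEAE summaries will be. One of the TEAE subgroups is "Subjects who received strong CYP3A4 inhibitors vs moderate CYP3A4 inhibitors vs none", and a matching line covers inducers. Both lines point to Section 5.10. That section names DrugBank as the source and states the rule: "The coded concomitant medications which contained below preferred terms will be marked according to type (inhibitor/inducer) and category (moderate/strong"), with an exception for topical, optic and aural routes. A closed table of terms follows. No SAP text brings in the protocol's lists or says what happens to a drug that the protocol names and 5.10 omits. Section 4 reports no change to the protocol-specified analyses.

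**The concern.** The subgroup tables are meant to show whether toxicity differs in patients who took a CYP3A4 modulator. The 'none' column is the reference and is defined by default: a patient is in it if no listed term of that type appears among the coded concomitant medications. If the list omits drugs that the protocol itself treats as modulators, the column can contain patients whom the protocol regards as exposed.

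Two outputs of the same report could then disagree. A patient who took rifabutin belongs in the protocol-deviation table as a user of a prohibited medication (SAP 2.4). With no other flagged inducer, the same patient appears in the inducer subgroup table as having taken none.

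**Working it through.** The plan states no figure on this point, so there is none to reproduce. The check compares two sets of names.

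**Inputs.** Set A is every drug in the four CYP3A4 inhibitor and inducer rows of protocol Tables 15 and 16, leaving out the fruits: 18 + 12 + 18 + 11 = 59. Set B is every term in SAP 5.10, of either type and category.

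**Matching rules, resolved in the SAP's favour.** Rifampin is matched to rifampicin and St. John's wort to Hypericum perforatum. Suboxone counts as captured through naloxone, because the rule catches any medication containing a listed term.

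| Protocol row | Named | No flag in 5.10 | Which |
|---|---|---|---|
| Moderate inhibitors (Table 15) | 18 | 8 | ciprofloxacin, metronidazole, cimetidine, zafirlukast, tofisopam, casopitant, cannabinoids, Schisandra sphenanthera |
| Moderate inducers (Table 15) | 12 | 6 | cotrimoxazole, mexiletine, metyrapone, genistein, ethosuximide, talviraline |
| Strong inhibitors (Table 16) | 18 | 1 | norfloxacin |
| Strong inducers (Table 16) | 11 | 3 | rifabutin, pioglitazone, troglitazone |
| Total | 59 | 18 | |

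- No flag of any kind: 18/59 = 30.5%.
- Moderate: (8 + 6)/(18 + 12) = 14/30 = 46.7%.
- Strong: (1 + 3)/(18 + 11) = 4/29 = 13.8%.
- No flag of the protocol's type: tipranavir is a moderate inducer in Table 15 but only a strong inhibitor in 5.10, so (18 + 1)/59 = 19/59 = 32.2%.
- If suboxone is not matched through naloxone, the two counts become 19/59 = 32.2% and 20/59 = 33.9%.

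**Shared drugs classed differently.** Atazanavir and darunavir are moderate in the protocol and strong in the SAP. Fluconazole, fluvoxamine, miconazole and avasimibe are strong in the protocol and moderate in the SAP. Suboxone, matched through naloxone, also moves from moderate to strong. Diltiazem appears in 5.10 as both moderate and strong, with no rule for choosing.

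**Extraction loss.** The 5.10 terms run alphabetically within each type and category, apart from the last two inducers. No gap is visible where the missing names would sit, so loss in reading the PDF is an unlikely explanation.

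**From names to patients.** A patient is placed in 'none' for a type only if every drug of that type they took is unlisted. TMP/SMX is the one unflagged drug whose use the protocol foresees in its own guidance. The documents give no concomitant-medication counts, so the number of patients affected cannot be computed.

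**The case against.** The strongest reply is that a prescribing list and an analysis list serve different purposes. Table 15 is offered as a guide that may not be exhaustive. SAP 5.10 names its own source, and the documents do not establish that the protocol's pharmacology is the right one. If some of the 18 drugs have little effect, moving their users out of 'none' would weaken the exposed groups instead. This stands as a reason not to call either list wrong. It does not explain the silence, because Table 15 also cites DrugBank among its sources and the SAP gives no reason for departing from the protocol's names.

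Four stronger readings are tempting, and the documents support none of them.

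- *A third of exposed patients are misclassified.* The 30.5% counts drug names. Use of most of them may be rare. The four unflagged strong agents are prohibited, and the Table 6 recommendations are not mandatory.
- *Every user of an unlisted drug lands in 'none'.* Section 5.10 flags loperamide as a strong inhibitor, and dexamethasone and glucocorticoids as strong inducers. The protocol recommends antidiarrheals early, permits steroids for bone metastases and suggests a dexamethasone mouth rinse for stomatitis. Some users of unlisted drugs will therefore be classed elsewhere.
- *The subgroup difference must shrink.* That requires unlisted drugs to act like listed ones. Under that assumption, with assumed TEAE rates of 40% in 'none' and 55% with a moderate inhibitor, contamination of 5%, 15% or 30% would turn 15 points into 14.25, 12.75 or 10.5. With an assumed 90 and 20 patients, the 95% half-width of the difference is 1.96 × √(0.24/90 + 0.2475/20), about 24 points, so even the largest shift would be lost in sampling error.
- *Prohibited use would go unreported.* SAP 2.4 tabulates CSR-reportable deviations, with a category for prohibited medication, and SAP 2.5.2 summarises on-treatment concomitant medication. The use would still appear there; only the subgroup label would conflict with it.

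**Conclusion.** The point holds as an inconsistency between two closed lists. On the matching rules above, 18 of the 59 protocol-named CYP3A4 inhibitors and inducers have no flag in SAP 5.10, and 19 have no flag of the protocol's type. The gap lies mainly among the moderate agents, whose use is allowed with caution. A patient whose only agent of a type is one of these drugs is labelled 'none', contrary to the protocol's classification. The size and direction of any bias cannot be derived from the documents, and they do not settle which classification is pharmacologically correct. The affected outputs are descriptive safety subgroups with no stated test or decision rule. The primary ORR analysis is unaffected, so this is a minor-to-moderate matter, worth correcting because it is cheap and because the tables are mandatory under SAP 2.2.8.

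**What to change.** Either of two changes would do.

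1. **Align the lookup.** Add the missing protocol-named drugs to the 5.10 table under their WHODrug names (for example sulfamethoxazole with trimethoprim for cotrimoxazole), add tipranavir as an inducer, and spell out which coded terms represent cannabinoids, which is a class. State one category rule for the drugs the two lists class differently (atazanavir, darunavir, fluconazole, fluvoxamine, miconazole, avasimibe, and suboxone if matched through naloxone) and for diltiazem, which the SAP lists twice. The sponsor must choose and record that rule.
2. **Keep the DrugBank list for the main tables**, say why it differs from Tables 15 and 16, and repeat the inhibitor and inducer subgroup tables with the protocol lists as a sensitivity analysis.

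In either case, report how many patients change group between the two lists. That supplies the figure which the documents cannot.

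The cost is an SAP appendix edit and a longer lookup table; no new data are needed. The downside of the first option is a slightly smaller 'none' group and possible dilution of the exposed groups by weak agents. The second option avoids that at the price of extra tables.
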